**NOTE: This section is designed to capture the out of pocket expenses associated with radiation therapy.**

How many hours were spent in total for each radiation treatment (time from leaving home/other accommodation or work to return to home/other accommodation or work)?

\_\_\_\_ (hours)

What is the distance from the radiation treatment facility from home/other accommodation or work? \_\_\_\_ (miles)

Did you commute daily to radiation treatment from your home?  Yes     No

Protocol name: NOVEMBER (Novem- (9), BrEast Radiation), A Phase II trial of a 9 day course of whole breast radiotherapy for early stage breast cancer.

Version Date: 23NOV2021

Principal Investigator: [name]

(If yes), method of transport used to get to the radiation therapy facility (Check all that apply)

Car  Yes  No

(If yes) approximate cost for parking per visit \$\_\_\_\_\_.\_\_\_\_

Did you drive yourself?  Yes  No

Were you driven?  Yes  No

Was it a combination of driving yourself or being driven  Yes  No

Shuttle  Yes  No

(If yes) Approximate cost per visit \$\_\_\_\_\_.\_\_\_\_

Public transport  Yes  No

(If yes) Approximate cost per visit \$\_\_\_\_\_.\_\_\_\_

On foot  Yes  No

Taxi/car service  Yes  No

(If yes) Approximate cost per visit (both ways) \$\_\_\_\_\_.\_\_\_\_

(If no), which of the follow apply (check one):

I was in a health care facility during radiation

I was living with a friend/family member during radiation (answer the commuting questions above)

I stayed hotel, apartment, or similar facility during radiation (answer the commuting questions above)

If hotel, apartment or similar facility, estimated cost of lodging during your radiation treatment \$\_\_\_\_\_.\_\_\_\_

Number of radiation treatments during which at least one other person accompanied patient \_\_\_\_

Number of visits to radiation treatment facility since completing radiation therapy (follow up visits) \_\_\_\_

Protocol name: NOVEMBER (Novem- (9), BrEast Radiation), A Phase II trial of a 9 day course of whole breast radiotherapy for

early stage breast cancer.

Version Date: 23NOV2021

Principal Investigator: [name]

From the 1st day of starting radiation, until 40 days after the completion of radiation:

Number of days the patient was unable to go to work at all \_\_\_\_

Number of days the patient went to work part-time \_\_\_\_

If part time, number of hours reduced from typical work day \_\_\_\_

Estimate child care costs due to radiation therapy \$\_\_\_\_, \_\_\_\_

Estimate wages lost due to radiation therapy \$\_\_\_\_, \_\_\_\_

Protocol name: NOVEMBER (November- (9), BrEast Radiation), A Phase II trial of a 9 day course of whole breast radiotherapy for

early stage breast cancer.

Version Date: 23NOV2021

Principal Investigator: [name]

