### 1.2 Secondary Objectives and Endpoint

1.2.1 To evaluate Breast-Q Patient Reported Outcomes (PROs) compared to historical control in breast conservation.

1.2.2 To evaluate the incidence of acute and late radiation complications, based on CTCAE 4.0 toxicity.

1.2.3 To evaluate the local and local regional recurrence rate.

1.2.4 To compare the direct and indirect patient costs for radiation therapy compared to historical controls as well as quality adjusted life years, utilizing the Breast-Q Patient Reported Outcomes (PROs) and the EQ-5D.

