## 7 STUDY CALENDAR

Laboratory and clinical parameters during treatment are to be followed using individual institutional guidelines and the best clinical judgment of the responsible physician. It is expected that patients on this study will be cared for by physicians experienced in the treatment and supportive care of patients on this trial.

Tests & Observations	Prior to Registration	Before RT	Weekly during RT	2 to 8 weeks post RT	6 months post RT*	12 months post RT*	2 years post RT*	3 years post RT**	5 years Post RT**
Obtain Informed Consent 	X								
H&P	X 								
Symptom Directed Physical 			X	X	X	X	X	X	
ECOG Performance Score	X		X	X	X	X	X	X	
Recurrence Assessment 					X	X	X	X	X 
Adverse Events Assessment 			X	X	X	X	X	X	X 
Photographic Cosmetic Assessment 		X					X		
Serum or Urine HCG	X 								
Breast-Q Survey 		X			X		X		
Health Care Expense Diary			X 						
Health Care Expense Survey				X 					
EQ-5D Survey 		X		X					

\* +/- 6 weeks

\*\* +/- 3 months

1. Assessment of side effects related to radiation therapy should be assessed according to the history and physical examination.
2. For women of childbearing potential. Must be done within 7 days prior to registration.
3. All screening procedures should be performed within 28 days prior to registration except as otherwise noted.
4. Health Care Expense Diary should be provided to the patient each week during RT to assist in recall for the Health Care Expense Survey after radiation completion. (Appendix III)
5. Post hoc chart review only for 5 years.
6. Photographic assessment collection will be done as described in section 8.1.
7. Breast Q Survey should be completed by the patient prior to radiation therapy and at 6 months post radiation therapy. (Appendix I)
8. Health Care Expense Survey should be completed using the Health Care Expense Diary worksheet (Appendix III) during the 2-8 week window and is found in Appendix II.
9. EQ-5D Survey should be completed by the patient prior to radiation therapy and during the post radiation therapy 2-8 week window. (Appendix IV)
10. Disease recurrence will be determined by standard of care assessments as described in section 8.3.

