### Health Care Expense Survey

Before you were diagnosed with breast cancer, did you do paid or unpaid work outside the home?

Yes     No

If you worked outside the home, which of the following best applies to you?

Paid work outside the home  Yes     No

Unpaid work outside the home  Yes     No (including work in a family farm or business).

Self-employed / business owner  Yes     No

If you worked outside the home:

How many days per week did you work? \_\_\_\_ (days)

How many hours per day did you work? \_\_\_\_ (hours)

What is your profession?

---

In what industry do you work?

---

What is / was your job title?

---

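### The survey's lost-work items run to day 40 after radiotherapy, but the single survey may be completed from day 14, so the secondary cost analysis can miss lost work; the diary and charge periods do not match it either

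*Combined protocol and SAP*

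**What the plan says.** Secondary objective 1.2.4 is "To compare the direct and indirect patient costs for radiation therapy compared to historical controls as well as quality adjusted life years". Five parts of the combined protocol and SAP set the periods over which costs are measured.

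- **Lost-work items (Appendix II).** Full days off, part-time days and hours reduced are asked for the period from the first "day of starting radiation, until 40 days after the completion of radiation". A screening question comes earlier: "Before you were diagnosed with breast cancer, did you do paid or unpaid work outside the home". The follow-up item, "Number of visits to radiation treatment facility since completing radiation therapy (follow up visits", has no fixed end date. The child-care item and "Estimate wages lost due to radiation therapy" come after the 40-day items, and the form does not make clear whether the 40-day period governs them.
- **Survey timing.** Footnote 8 of the Study Calendar has the survey completed, with the diary as worksheet, "during the 2-8 week window and is found in Appendix II". Footnote 12 and section 8.4 give the comparison patients the same window. The calendar shows one survey.
- **Diary.** Footnote 4 says the "Health Care Expense Diary should be provided to the patient each week during RT to assist in recall for the Health Care Expense Survey". Section 8.4 has it filled in weekly during RT. Appendix III tells patients to keep it until 6 to 10 weeks after RT. Section 8.4 gives the comparison patients the survey but does not mention a diary for them.
- **Charges.** Section 8.4 counts charges from registration until 2 to 8 weeks after RT.
- **Use.** Section 9.2.4 converts time spent on treatment, travel and lost productivity to cost. Section 2.6 models direct costs with a time-on-study term and baseline covariates.

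**The concern.** A compliant survey can be completed before the period it asks about has ended. A patient surveyed at two weeks cannot report absence in weeks three to six. Nothing in the document requires completion on or after day 40, a second survey, a call-back or a correction for early completion.

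The people exposed are those who worked before diagnosis and who lose work time after an early survey. Their lost productivity is understated, and that quantity feeds the indirect-cost side of objective 1.2.4. Section 8.4 names less time off and a faster return to work among the expected benefits of the short course, and any part of that difference that falls after the survey day is not seen.

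The other periods do not repair this. The diary has two stated durations, and the longer one can outlast the last permitted survey. The charge period starts at an event that the comparison patients do not have, and it ends anywhere within a six-week range. Direct and indirect costs can therefore cover different stretches of time, both within one patient and between groups.

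**Working it through.** The plan gives no figure on this point to reproduce. The check is a comparison of time windows. Days are counted from the last fraction, and 2-8 weeks is read as days 14-56.

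**Inputs**
- End of the lost-work period: day 40 (Appendix II).
- Survey window: days 14-56, both groups (section 7, footnotes 8 and 12; section 8.4).
- End of diary: days 42-70, that is 6-10 weeks (Appendix III), or weekly during RT (section 8.4).
- End of charges: days 14-56 (section 8.4).

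**Step 1. Days not yet observed.** Unobserved days = max(0, 40 − survey day).

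| Survey day | Unobserved post-RT days | Share of 40 |
|---|---|---|
| 14 | 26 | 65% |
| 21 | 19 | 47.5% |
| 28 | 12 | 30% |
| 35 | 5 | 12.5% |
| 40 or later | 0 | 0% |

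**Step 2. Average, under an assumption.** Completion dates are not given. If surveys were spread evenly over days 14-56 (assumption), the share completed before day 40 would be (40 − 14)/(56 − 14) = 26/42 = 62%. The mean number of unobserved days over all surveys would be 0.619 × 13 = 8.05, about 8 calendar days.

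**Step 3. From calendar days to workdays.** Unobserved days are not lost workdays. For a Monday-to-Friday worker (assumption), days 15-40 hold 18 or 19 workdays, depending on the weekday of the last fraction; that is the most that could be missed. As an illustration (assumption), take a worker who is off until day 28:
- surveyed at day 14: days 15-28 are missed, 10 workdays;
- surveyed at day 21: days 22-28 are missed, 5 workdays;
- surveyed at day 28 or later: none missed.

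A patient who did not work, or who was back at full hours by the survey day with no later absence, has a complete count at any survey date.

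**Step 4. Diary against survey.** The Appendix III diary ends 42 − 14 = 28 to 70 − 14 = 56 days after the earliest permitted survey, and up to 70 − 56 = 14 days after the latest. Appendices II and III fit each other, because day 40 falls before day 42; the misfit is with the survey window. Only days 42-56 lie in both stated ranges.

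**Step 5. Charges.** The post-RT charge period can be 14 to 56 days, a ratio of 56/14 = 4.

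**The case against.** The best defence is that both groups complete the survey in the same window and that section 8.4 matches the comparison patients on travel distance and employment status. With similar survey timing and similar late absence, the loss falls on both groups and need not bias the difference. Sites could also, within the rules, run every survey late in the window. The time-on-study term in section 2.6 may absorb part of the variation in charge period. Section 9.2.4 presents the cost-effectiveness work as exploratory. All of this stands, and it limits the consequence. It does not remove the mismatch: the matching covers neither survey timing nor absence after the survey, late completion is not required, and time on study is not defined for patients who never enrol.

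On the diary, footnote 4 says when it is handed out, not when recording stops. The clear conflict is between section 8.4 and Appendix III.

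Three stronger readings are tempting, and the documents do not support them:

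- *The comparison is biased in a known direction, for instance by hiding the benefit of the short course.* The documents give no survey dates and no data on return to work, so neither sign nor size can be fixed.
- *Early surveys lose 26 days of work.* These are calendar days not yet observed; many patients will have lost none of them.
- *The comparison is confounded by chemotherapy.* Section 8.4 allows comparison patients who are ineligible for the trial, so some might have had chemotherapy before RT, which exclusion 4.2.8 bars. No number is given, section 2.6 plans baseline adjustment for direct costs, and this is a question of who is compared rather than of time windows. It is not part of this point.

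**Conclusion.** The mismatch is plain in the text and should be corrected. A compliant survey on days 14 to 39 leaves up to 26 of the 40 post-RT days unobserved, and later lost work is not counted. The diary has two conflicting durations. The charge period has no defined start for the comparison patients and can vary fourfold after RT.

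Confidence is high for the mismatch and lower for its effect. What follows directly is incomplete capture whenever work is lost after an early survey, with added noise in indirect costs. Bias between groups is a risk if survey timing, late absence or charge-period length differs between them. The 62% and 8-day figures rest on an even spread of survey dates, and the workday example is hypothetical. Only the secondary cost analysis is affected; the primary cosmetic endpoint and its sample size are not.

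**What to change.** 1. **Survey.** Have both groups complete it on days 40-56, inside the existing window (days 42-56 if the Appendix III period is kept). Alternatively, end the lost-work items at day 14, so that every permitted survey has reached the end of the period. Give the follow-up-visit, child-care and wage items the same stated period. *Cost:* the first option removes 43 − 17 = 26 permitted survey days (days 14-39) and may separate the survey from the EQ-5D, which is also due "during the post radiation therapy 2-8 week window". It may also capture absence due to chemotherapy, which section 5.2 allows from 10 days after the last fraction; state this as a limitation. The second option captures loss over a shorter period.

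2. **Surveys already collected.** Keep the raw counts, and add a sensitivity analysis limited to surveys completed on or after day 40. Do not divide by days observed. Nine workdays missed during an 11-day course is a correct count at any survey date, yet it would become 9/(11 + 14) = 0.36 per day at day 14 and 9/(11 + 40) = 0.18 at day 40. *Cost:* a smaller sample. The form carries a completion date but no RT end date, so the last-fraction date must be obtained for comparison patients. That may take effort, since section 2.6 describes them as de-identified.

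3. **Diary.** Reconcile section 8.4 and Appendix III with the survey period. Give comparison patients the diary, or state the difference in recall aids as a limitation.

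4. **Charges.** In both groups, count from one common pre-RT start that includes treatment planning to one fixed day after the last fraction. Starting at the first fraction would drop any planning charges that now fall after registration. Show results with and without chemotherapy charges, because a longer fixed period can bring more of them in. If time on study stays in the section 2.6 model, define it for both groups.

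Apart from the RT end dates and any diaries for comparison patients, this is a change to form and protocol wording. No extra clinic visit is needed if the survey can be completed away from the clinic.

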### Appendix III - HEALTH CARE EXPENSE DIARY FOR SURVEY COMPLETION

Use this diary to record your health care-related expenses from the time you start radiation therapy until 6 to 10 weeks after you have completed radiation therapy. A copy of the survey questions is included with this diary for your reference.

Protocol name: NOVEMBER (Novem- (9), BrEast Radiation), A Phase II trial of a 9 day course of whole breast radiotherapy for

## early stage breast cancer. Using *BRCA1* to

Version Date: 23NOV2021

Principal Investigator: [name]

Protocol name: NOVEMBER (Novem- (9), BrEast Radiation), A Phase II trial of a 9 day course of whole breast radiotherapy for early stage breast cancer.

Version Date: 23NOV2021

Principal Investigator: [name]

## **Appendix IV – EQ-5D-3L**

# **NOVEMBER**

## **EQ-5D-3L**

**Patient Study ID:** 103976-01-\_\_\_\_\_

**Patient Initials:** \_\_\_\_\_

**Date of Completion:** \_\_\_\_\_ / \_\_\_\_\_ / \_\_\_\_\_

Protocol name: NOVEMBER (Novem- (9), BrEast Radiation), A Phase II trial of a 9 day course of whole breast radiotherapy for

early stage breast cancer.

Version Date: 23NOV2021

Principal Investigator: [name]

## **Health Questionnaire**

**English version for the USA**

USA (English) © 1998 EuroQol Group EQ-5D™ is a trade mark of the EuroQol Group

By placing a checkmark in one box in each group below, please indicate which statements best describe your own health state today.

**Mobility**

I have no problems in walking about

I have some problems in walking about

I am confined to bed

**Self-Care**

I have no problems with self-care

I have some problems washing or dressing myself

I am unable to wash or dress myself

**Usual Activities** (e.g. work, study, housework, family or leisure activities)

I have no problems with performing my usual activities

I have some problems with performing my usual activities

I am unable to perform my usual activities

**Pain / Discomfort**

I have no pain or discomfort

I have moderate pain or discomfort

I have extreme pain or discomfort

**Anxiety / Depression**

I am not anxious or depressed

I am moderately anxious or depressed

I am extremely anxious or depressed

Protocol name: NOVEMBER (Novem- (9), BrEast Radiation), A Phase II trial of a 9 day course of whole breast radiotherapy for

early stage breast cancer.

Version Date: 23NOV2021

Principal Investigator: [name]

To help people say how good or bad a health state is, we have drawn a scale (rather like a thermometer) on which the best state you can imagine is marked 100 and the worst state you can imagine is marked 0.

We would like you to indicate on this scale how good or bad your own health is today, in your opinion. Please do this by drawing a line from the box below to whichever point on the scale indicates how good or bad your health state is today.

Your own health  
state today

Best imaginable  
health state

100

90

80

70

60

50

40

30

20

10

Worst imaginable  
health state

Protocol name: NOVEMBER (Novem- (9), BrEast Radiation), A Phase II trial of a 9 day course of whole breast radiotherapy for early stage breast cancer.

Version Date: 23NOV2021

Principal Investigator: [name]

## Appendix V – ECOG/KPS Conversion

ECOG PERFORMANCE STATUS	KARNOFSKY PERFORMANCE STATUS
0—Fully active, able to carry on all pre-disease performance without restriction	100—Normal, no complaints; no evidence of disease  90—Able to carry on normal activity; minor signs or symptoms of disease
1—Restricted in physically strenuous activity but ambulatory and able to carry out work of a light or sedentary nature, e.g., light house work, office work	80—Normal activity with effort, some signs or symptoms of disease  70—Cares for self but unable to carry on normal activity or to do active work
2—Ambulatory and capable of all selfcare but unable to carry out any work activities; up and about more than 50% of waking hours	60—Requires occasional assistance but is able to care for most of personal needs  50—Requires considerable assistance and frequent medical care
3—Capable of only limited selfcare; confined to bed or chair more than 50% of waking hours	40—Disabled; requires special care and assistance  30—Severely disabled; hospitalization is indicated although death not imminent
4—Completely disabled; cannot carry on any selfcare; totally confined to bed or chair	20—Very ill; hospitalization and active supportive care necessary  10—Moribund
5—Dead	0—Dead

\*\*Zubrod C, et al. Appraisal of methods for the study of chemotherapy in man: Comparative therapeutic trial of nitrogen mustard and thiophosphoramide. *Journal of Chronic Diseases*; 1960:11:7-33.
